6. ERYTHROPOIESIS-STIMULATING AGENTS AND PARENTERAL IRON DOSES

ESA dosing will be summarized separately for EPOGEN (epoetin alfa), ARANESP (darbepoetin alfa) and MIRCERA (methoxy polyethylene glycol-epoetin beta) respectively. Historic ESA doses prior to randomization will be summarized weekly by treatment group for the pharmacodynamic analysis population. The mean weekly dose from Week -10 through Week -1 will also be computed for all ESAs. Percent change from baseline in ESA dose, change in ESA dose with ESA normalized to EPOGEN units, and change in ESA to a threshold value will also be computed with all ESAs pooled.

The following analyses will be performed:

- Comparison of the mean weekly ESA dose expressed in EPOGEN units prior to randomization to the post-randomization mean weekly dose for each 4-week interval in the Treatment and Safety Follow-up periods (e.g. Weeks 1-4, 5-8, etc). Inferential statistics will be performed for the Week 8-12 and the Week 1-4 periods.
 - Conversion of MIRCERA and ARANESP doses to EPOGEN units will be as follows:

$$\text{MIRCERA or ARANESP dose in mcg} * 300 = \text{EPOGEN unit equivalent dose}$$

- The percentage change from baseline with all 3 ESAs combined will be calculated for each 4-week interval in the Treatment and Safety Follow-up periods (e.g. Weeks 1-4, 5-8, etc). Inferential statistics will be performed for the Week 8-12 and the Week 1-4 periods.
- The number and percentage of subjects with dose change by +/- $\geq 25\%$, +/- $\geq 50\%$, and +/- $\geq 100\%$ will be computed for each 4-week interval in the Treatment and Safety Follow-up periods (e.g. Weeks 1-4, 5-8, etc).

Calculation of the Baseline ESA Dose

The baseline dose will be the baseline mean weekly dose for each ESA as defined below multiplied by 4.

- For EPOGEN, the baseline will be the mean weekly dose based on the 2 weeks immediately prior to randomization multiplied by 4.

- For ARANESP and MIRCERA, the baseline will be the mean weekly dose based on the 2 doses immediately prior to randomization multiplied by 4.
- The baseline dose will be normalized as the average dose per week during the time period of the doses used to define the baseline multiplied by 4.

Calculation of the Post-Baseline ESA Dose

- The post-baseline dose will be calculated based on the sum of all doses during a given time interval and will be expressed as the average dose per week during that time period multiplied by 4 or the number of weeks in the interval.
- The intervals that will be described are Weeks 1-4, 5-8, 9-12, etc through Week 24. In addition, Weeks 8-12 (the endpoint) and Weeks 1-12 will be described.

Parenteral iron doses are generally expected to be administered weekly, every other week, or with each dialysis. Parenteral iron doses will be summarized based on elemental iron contained within the iron product administered. All parenteral iron products will be combined for the analyses. If dose units are reported in mL, these will be converted to mg of elemental iron as follows:

IRON PRODUCT	ELEMENTAL IRON
Ferric gluconate (e.g. Ferrlecit)	12.5 mg per mL
Ferumoxytol (e.g. Feraheme)	30 mg per mL
Ferric carboxymaltose (e.g. Ferinject)	50 mg per mL
Ferric pyrophosphate citrate (e.g. Triferic)	5.44 mg per mL
Iron sucrose (e.g. Venofer)	20 mg per mL

Post-randomization parenteral iron doses will be summarized in a similar way to ESA. No analyses will be performed using individual parenteral products, however.

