No change in the total weekly dose during Week -1 compared with Week -2.
 - For ESAs dosed less often than weekly:***
Any dose given during Full Screening Week -2 and Week -1 is unchanged from the immediately preceding dose.
 - Note: If a dose was given on both Week -2 and Week -1, then both doses are the same. (These 2 doses may be different than earlier doses).

10. Has been receiving intravenous (IV) or dialysate iron regularly and continuously (e.g., with each dialysis or each week) during the 3 weeks prior to randomization OR has received no IV or dialysate iron during this time frame and use of IV or dialysate iron is not anticipated through Study Week 24.
 - If parenteral iron has been administered during the 3 weeks prior to randomization, the regimen has been stable (same elemental iron dose, same frequency, and same iron product) with no more than 2 missed or held doses if dosed with each dialysis and no missed or held doses (if dosed weekly or less frequently) during this time frame.

11. If receiving oral ferric citrate, the patient has been prescribed it for at least 2 weeks prior to Full Screening and the dose is not anticipated to be changed through Study Week 24.

12. At least 2 ferritin values during Screening > 300 ng/mL.

13. At least 2 TSAT values during Screening between 15% and 50% (inclusive).

14. ESA resistance index (confirmed by the Sponsor) during the 2 weeks prior to randomization:

For patient receiving epoetin alfa:

$$\frac{\text{Total weekly dose of epoetin alfa (units)}}{(\text{hemoglobin [g/dL]} * \text{target dry body weight [kg]})} > 8 \text{ units/kg per g/dL}$$

For patients receiving darbepoetin alfa:

$$\frac{\text{Total weekly dose of darbepoetin alfa (mcg) * 300}}{(\text{hemoglobin [g/dL]} * \text{target [kg]})} > 8 \text{ units/kg per g/dL}$$

For patients receiving methoxy polyethylene glycol-epoetin beta:

$$\frac{\text{Weekly dose of methoxy polyethylene glycol-epoetin beta (mcg) * 300}}{(\text{hemoglobin [g/dL]} * \text{target dry body weight [kg]})} > 8 \text{ units/kg per g/dL}$$

If the ESA is dosed less often than once a week, divide the dose by the dosing interval to determine the weekly dose. For example, Weekly dose = dose given every two weeks ÷ 2.

The first day of each week used for calculations is defined as the first dialysis day of the Week (i.e., Monday or Tuesday).

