Appendix C ESA and Parenteral Iron Dose-Adjustments

Weeks 1 - 4

- ESA doses are not to be adjusted or held during Weeks 1 through 4 unless one or more confirmed hemoglobin values (i.e., at least 2 consecutive measurements) or the patient's clinical status necessitates such due to a clear and present safety risk
- Parenteral iron doses are not to be adjusted or held during Weeks 1 through 4
- Patients not receiving parenteral iron products during Screening must not be started on these during Weeks 1 through 4
- The Medical Monitor must be contacted prior to any contemplated ESA or parenteral iron dose changes

Weeks 5 – 24

- Changes to ESA dosing must be based on hemoglobin values that have been confirmed (i.e., at least 2 consecutive measurements)
- Do not increase the dose more frequently than once every 4 weeks. The recommended dose increase at any given time is 25%
- Decreases in dose may occur more frequently than once every 4 weeks. The recommended minimum duration between dose reductions is 3 weeks
- If the hemoglobin rises rapidly (e.g., more than 1 g/dL in any 2-week period), reduce the dose by 25%. A greater reduction may be made, if rise in hemoglobin is unacceptably rapid
- The Medical Monitor must be contacted prior to any contemplated ESA dose changes that depart from the above protocol requirements and recommendations unless clinical urgency precludes this. If the Medical Monitor is not contacted in advance, please send a notification within 24 hours that an off-protocol ESA dose change was made
- Patients not receiving parenteral iron products must not be started on these during Weeks 5 through 24
- Parenteral iron doses are not to be adjusted or held during Weeks 5 through 24, unless approved by the Medical Monitor

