7.3 OTHER EFFICACY ANALYSES

Additional secondary objective is to explore the pharmacodynamic effects of COR-001 compared to placebo by evaluating changes in

- Change in hemoglobin from screening to peak hemoglobin (defined as per subject absolute maximal hemoglobin in g/dL)
- ERI and Hemoglobin from baseline (weekly mean during the Screening Period for ERI and mean of Full Screening and Day 1 for Hemoglobin) through Week 4, 12 and 24
- ERI and Hemoglobin from baseline (weekly mean during the Screening Period for ERI and mean of Full Screening and Day 1 for Hemoglobin) through Week 4, 12 and 24 stratified by baseline ERI tertiles
- ESA and parenteral iron dose requirements from baseline (weekly mean during the Full Screening Period) to Evaluation Period (Weeks 8 – 12) and through Week 24.

- Systemic iron stores (serum ferritin, hepatic and splenic iron content, and supplemental iron dose requirements) over time
 - Markers of malnutrition-inflammation (pre-albumin and albumin) over time
 - LV mass index from Screening to Week 12
 - Pre-dialysis, post-dialysis, and delta-serum Troponin and NT-proBNP (defined as the difference between the pre- and post-dialysis troponin) from baseline (mean of Screening) to Weeks 10 – 11.
 - Handgrip strength from baseline (during screening) to Week 12
- FACIT fatigue score from baseline (during screening) to Week 12

For the above efficacy variables, the observed values and changes from baseline will be summarized by treatment group using descriptive statistics for Pharmacodynamic analysis population.

Specifically, the weekly mean of ERI will be calculated and presented individually for each ESA based on the formula in [Section 1.2.3.2](#).

The mean of left and right handgrip strengths will be used for analysis no matter which hand is dominant.

The FACIT-F (Version 4) is a compilation of general questions divided into five primary domains: Physical Well-Being, Social/Family Well-Being, Emotional Well-Being, Functional Well-Being and Additional Concerns. The data in Additional Concern domain will be listed separately and considered the primary analysis for the FACIT-F. The total fatigue score will be calculated as a summation of the scores in the five primary domains. The observed value and change from baseline in total fatigue score will be summarized by treatment.

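### SAP 6 promises inference on ESA dose but specifies no COR-001 versus placebo test; its first analysis is worded as dose before versus after randomization

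*SAP*

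**What the plan says.** SAP section 6 lists three ESA-dose analyses.

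- The first is a "Comparison of the mean weekly ESA dose expressed in EPOGEN units prior to randomization to the post-randomization mean weekly dose", for each 4-week interval.
- The second reads "The percentage change from baseline with all 3 ESAs combined will be calculated for each 4-week interval".
- The third counts patients whose dose changes by set percentages.

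Each of the first two is followed by the sentence "Inferential statistics will be performed for the Week 8-12 and the Week 1-4 periods". No test, model, comparator or significance level is named in either place. The same section calls Weeks 8-12 the endpoint.

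SAP 7.3 gives the purpose: to "explore the pharmacodynamic effects of COR-001 compared to placebo by evaluating changes in" a list of variables that includes "ESA and parenteral iron dose requirements from baseline (weekly mean during the Full Screening Period) to Evaluation Period (Weeks 8 – 12"). The method stated there is descriptive statistics by treatment group.

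SAP 7.1 and 7.2 specify an ANCOVA with dose group as factor and baseline value as covariate, reporting least-squares mean differences from placebo with 95% confidence intervals and p-values. It covers hsCRP, SAA, free IL-6, hemoglobin, ERI, TSAT, CHr, pre-albumin and albumin. ESA dose is not on the list.

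**The concern.** The question is whether COR-001 changes ESA requirement relative to placebo. A test of dose after randomization against dose before it has a different null hypothesis: that mean dose is constant over time. That null can be false in both arms with no drug effect, and the documents contain two reasons why it might be.

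- **Selection at entry.** Protocol 4.1, inclusion criterion 14, requires an "ESA resistance index (confirmed by the Sponsor) during the 2 weeks prior to randomization" above 8 units/kg per g/dL. ESA dose is the numerator of that index, and for EPOGEN the SAP 6 baseline is the mean weekly dose over the same 2 weeks. Some regression to the mean is possible.
- **Retitration.** From Week 5, Protocol Appendix C lets ESA dose follow hemoglobin in both arms. Increases are limited to one every 4 weeks; decreases may come more often.

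A significant fall within COR-001 could therefore be reported as an ESA-sparing effect when placebo fell equally. If doses drift upward instead, a real sparing effect could be hidden. The percent-change analysis has the same problem if it is read as a test against zero.

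For Weeks 1-4 inference has little to work on, because Appendix C says "ESA doses are not to be adjusted or held during Weeks 1 through 4" except where confirmed hemoglobin values or the patient's clinical status create a clear safety risk.

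**Working it through.** **Is there a figure to reproduce?** No. Neither document gives a sample size, power or significance level for ESA dose. Two-sided 0.05 is stated for the sample-size calculations only (Protocol 11.1, SAP 1.3.2) and is assumed here.

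**Inputs**

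- About 60 patients in up to 6 cohorts (Protocol synopsis), allocated 8:2 (Protocol 3.2 and 3.3.1). This gives 6 × 8 = 48 COR-001 and 6 × 2 = 12 placebo. Two cohorts at one dose give 16 COR-001 patients.
- Drift δ, the mean change in SDs of change, equal in both arms, with no drug effect. The documents do not give it. Assumed range: 0 to 0.5.

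**Pre/post test within one arm.** The statistic is mean change ÷ (s/√n). Under drift δ it follows a noncentral t distribution with n − 1 degrees of freedom and noncentrality δ√n, so

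P(reject) = P(|T(n−1, δ√n)| > t(0.975, n−1)).

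For n = 48 the critical value is 2.012, and δ√48 = 1.386, 2.078 and 3.464 for δ = 0.2, 0.3 and 0.5.

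**COR-001 versus placebo.** A two-sample t-test on change, 48 versus 12, with 40,000 simulated trials per setting. The common drift cancels in the difference.

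| Probability of p < 0.05, no drug effect | δ = 0 | 0.2 | 0.3 | 0.5 |
|---|---|---|---|---|
| Pre/post, COR-001, n = 48 | 5% | 27% | 53% | 92% |
| Pre/post, one dose group, n = 16 | 5% | 12% | 20% | 46% |
| Pre/post, placebo, n = 12 | 5% | 10% | 16% | 35% |
| COR-001 significant, placebo not | 5% | 25% | 45% | 60% |
| COR-001 versus placebo, 48 versus 12 | 5% | 5% | 5% | 5% |

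The fourth row shows that setting the two arms' pre/post p-values side by side is no remedy. With 48 against 12 patients, the same drift is often significant in one arm and not in the other.

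**How much could selection alone produce?** This was simulated with log-normal doses, between-patient log-SD 0.6, equal within-patient noise before and after, and n = 48. All of these inputs are assumptions.

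- Within-patient log-SD 0.2 to 0.4, entry limited to the top 50% or 30% on baseline dose: the paired test rejects in about 11% to 51% of trials.
- Within-patient log-SD 0.1, same entry limits: about 6% to 9%.
- Weak selection (top 80%): about 5% to 6%.

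So the inflation can be substantial or negligible, depending on inputs the documents do not supply.

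**The case against.** The best reply is that SAP 6 leaves the contrast open and does not choose a wrong one. Comparing dose before with dose after may only describe how the change is derived, with the arms then compared. The context supports this reading: SAP 2.1 summarizes by treatment group with placebo pooled, SAP 7 pools COR-001 and placebo for the pharmacodynamic analyses, and SAP 7.3 states the placebo comparison as the aim. The table shells are in a separate document. This stands in part. A between-group test is not excluded, but none is specified, and the literal wording of the first analysis is pre versus post.

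A reader might go further and infer any of the following. The documents do not support them.

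- *The pre/post comparison is the only inference planned on ESA dose.* Two analyses promise inference, and the second leaves its contrast open.
- *The randomized control is not used for ESA requirement.* ERI, which contains ESA dose, is a secondary endpoint compared with placebo by ANCOVA in SAP 7.2. ESA dose requirement itself is in the exploratory lists of Protocol 3.1.3 and SAP 1.2.3.2.
- *Weeks 1-4 cannot show a drug effect.* Appendix C restricts ESA changes in that period but does not exclude them. A confirmed hemoglobin rise could trigger the safety exception.
- *Doses will fall without a drug effect.* Dose had to be stable at entry (criteria 8 and 9), and no change was anticipated in Weeks 1-4 (criterion 16). Patients enter with hemoglobin of 8.5 to 11.0 g/dL, so titration could also raise doses.

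**Conclusion.** The point holds as a defect of specification with a real risk attached. SAP 6 commits to p-values on ESA dose, its first analysis is worded as a within-patient comparison over time, and no COR-001 versus placebo test of ESA dose appears in either document. The tabulated error rates rest on an equal drift in both arms, approximately normal change, two-sided 0.05 and all six cohorts filled. With zero drift the pre/post test keeps its 5% level; it would still test change over time and not the difference from placebo. The consequence is limited to an exploratory endpoint and does not touch the primary safety objective or the ERI analysis. It is still worth correcting, because a reported fall in ESA dose is easily taken as evidence of drug effect.

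**What to change.** In SAP 6, state that inference on ESA dose for Weeks 8-12 compares COR-001 with pooled placebo, using the SAP 7.2 ANCOVA. The outcome is change in mean weekly EPOGEN-equivalent dose. Treatment is the factor (pooled COR-001 versus pooled placebo, then by dose), and baseline mean weekly dose is the covariate. Report the COR-001 minus placebo difference with its 95% confidence interval and p-value.

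Keep within-group change and percent change descriptive. Make Weeks 1-4 descriptive too, as a record of how far the Appendix C restriction was followed. SAP 6 says parenteral iron will be summarized in a similar way, so if inference is carried over to iron, the same rule should apply.

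The cost is a change of SAP wording and one more use of a model already specified for other endpoints. The statistical price is precision. In SDs of change, before any gain from the baseline covariate, the standard error is √(1/48 + 1/12) = 0.323 for the difference, against 1/√48 = 0.144 for change within COR-001, about 2.2 times as large. With 12 placebo patients, 80% power needs a true difference of roughly (1.96 + 0.84) × 0.323 = 0.90 SD. The wider interval is the honest one for the question asked.

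### SAP 6 averages post-baseline ESA dose over calendar weeks, so in the five-week Weeks 8-12 window an unchanged every-2-week ESA shows a false change of +20% or -20%; the multiplier is also left open

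*SAP*

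**What the plan says.** **Baseline (SAP 6).** For the two longer-acting agents: "For ARANESP and MIRCERA, the baseline will be the mean weekly dose based on the 2 doses immediately prior to randomization multiplied by 4". A further bullet adds: "The baseline dose will be normalized as the average dose per week during the time period of the doses used to define the baseline", again multiplied by 4. The denominator is the time that the doses cover, so the result follows the dosing interval.

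**Post-baseline (SAP 6).** "The post-baseline dose will be calculated based on the sum of all doses during a given time interval", and the same sentence goes on to say that it "will be expressed as the average dose per week during that time period multiplied by 4 or the number of weeks in the interval". Here the denominator is the number of calendar weeks in the window. Nothing says when the multiplier is 4 and when it is the number of weeks.

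**Windows (SAP 6).** After the consecutive 4-week intervals, the SAP adds: "In addition, Weeks 8-12 (the endpoint) and Weeks 1-12 will be described". On testing: "Inferential statistics will be performed for the Week 8-12 and the Week 1-4 periods". This applies both to the mean weekly dose in EPOGEN units and to the percentage change with the three ESAs combined.

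**Dosing interval (Protocol 4.1).** Criterion 9 admits ESAs given less often than weekly. Criterion 14 gives the conversion for eligibility: "If the ESA is dosed less often than once a week, divide the dose by the dosing interval to determine the weekly dose". Its worked example is a dose given every two weeks.

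**The concern.** Baseline and post-baseline doses should differ only if the patient's dosing changed. Here they use different denominators. For an ESA given every two weeks or less often, the number of doses in a fixed calendar window can differ by one according to where the schedule falls. When the window is not a whole number of dosing intervals, that one dose produces an apparent change in a patient whose regimen has not changed.

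This matters because lower ESA need is part of the rationale for the drug (Protocol 1.1 and 3.7), Weeks 8-12 is one of only two ESA periods to be tested, and patients who are affected are pooled with patients who are not. Protocol Appendix C recommends dose steps of 25%, so a 20% artefact is close in size to one real step.

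**Working it through.** The documents give no figure for this point, so there is none to reproduce. The check is a count of doses.

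**Inputs**
- Constant dose D every k weeks, given on schedule. k = 2 is the example in criterion 14. k = 4 is an assumption: less-than-weekly dosing is allowed without an upper limit, but no section names four weeks.
- Baseline per week (SAP 6), taking each dose to cover one interval: 2D/(2k) = D/k.
- Post-baseline per week (SAP 6): nD/W, with n doses falling in a window of W weeks.
- Weeks 8-12 = Weeks 8, 9, 10, 11 and 12, so W = 5 (Days 50 to 84).

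**Formula.** With the same multiplier on both sides, false change = (nD/W)/(D/k) - 1 = nk/W - 1.

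**Weeks 8-12, W = 5**

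| Schedule | Doses in window | n | False change | Share of phases |
|---|---|---|---|---|
| Weekly | every week | 5 | 5 x 1/5 - 1 = 0% | all |
| Every 2 weeks | Weeks 8, 10, 12 | 3 | 3 x 2/5 - 1 = +20% | 1/2 |
| Every 2 weeks | Weeks 9, 11 | 2 | 2 x 2/5 - 1 = -20% | 1/2 |
| Every 4 weeks (assumed) | Weeks 8, 12 | 2 | 2 x 4/5 - 1 = +60% | 1/4 |
| Every 4 weeks (assumed) | Week 9, 10 or 11 | 1 | 1 x 4/5 - 1 = -20% | 3/4 |

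Counting from every possible starting day gives the same values and shares. No patient on either longer schedule can show the true 0%.

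**Mean and spread over phases**
- Every 2 weeks: mean (20 - 20)/2 = 0; SD 20 points.
- Every 4 weeks: mean 0.25 x 60 - 0.75 x 20 = 0; SD = sqrt(0.25 x 60² + 0.75 x 20²) = sqrt(1200) = 34.6 points.

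**Other windows, exact schedule**
- Weeks 1-4, 5-8 and 9-12 (W = 4): k = 2 gives 2 x 2/4 - 1 = 0; k = 4 gives 1 x 4/4 - 1 = 0.
- Weeks 1-12 (W = 12): 6 x 2/12 - 1 = 0 and 3 x 4/12 - 1 = 0.
- These zeros need exact timing. In a simulation with each dose shifted independently by up to 2 days, about 10% of every-2-week patients showed ±50% in Weeks 1-4, and about 5% of every-4-week patients showed ±100%.

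**Multiplier.** If Weeks 8-12 is multiplied by 5 while baseline is multiplied by 4, every ratio is scaled by 5/4:
- weekly: 1.00 x 1.25 = 1.25, so +25% for everyone;
- every 2 weeks: 1.2 x 1.25 = 1.50 or 0.8 x 1.25 = 1.00, so +50% or 0%;
- every 4 weeks: 1.6 x 1.25 = 2.00 or 0.8 x 1.25 = 1.00, so +100% or 0%.

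The mean is then +25% on all three schedules.

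**Weight in the comparison.** Placebo is pooled over cohorts (SAP 1.2.3, 2.1 and 7): 2 per cohort x 6 cohorts = 12 if all six enrol. One placebo patient at +60% moves that mean by 60/12 = 5 points; one at ±20% moves it by 20/12 = 1.7 points.

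**The case against.** **The window might mean 28 days.** SAP 6 mentions Weeks 8-12 in bullets about 4-week intervals, and the Week 8 and Week 12 visits (Days 50 and 78) are 28 days apart. On that reading the artefact is 0%. It does not fit the text: Weeks 8-12 is listed in addition to the 4-week intervals, which already include Weeks 9-12, and the scaling rule provides for intervals that need their own number of weeks.

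**The endpoint is exploratory.** This stands. Protocol 3.1.3 and the SAP's exploratory list place ESA dose requirement there, and SAP 7.3 summarises it descriptively. The inferential statistics come from SAP 6 alone. The dose-change categories from 25% upwards are set for 4-week intervals, so they are free of the artefact when doses are on schedule.

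**It is noise, not bias.** With a common multiplier this also stands. Nothing in the documents links dose phase to treatment arm, and the mean error over phases is zero.

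Four stronger readings are tempting, and the documents do not support them:
- From the opening clause alone, a reader might infer that the post-baseline dose is an unscaled sum. The rest of the sentence converts it to an average per week.
- The +60% might be taken as the typical size. It needs an every-4-week schedule that the documents do not name, and then only one phase in four.
- A reader might set the effect against two placebo patients per cohort. The final analysis pools placebo.
- A reader might carry the fault over to ERI at Weeks 10-12. No section says that the SAP 6 dose sum feeds ERI; SAP 1.2.3.2 uses a weekly dose, and SAP 7.2 ties screening ERI to criterion 14. The gap is only that SAP 1.2.3.2 does not repeat the divide-by-interval rule for post-baseline values.

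**Conclusion.** The concern holds in a limited form. Followed as written, SAP 6 gives a wrong patient-level value in a window that is to be tested. The size is ±20% for an unchanged every-2-week ESA and, if every-4-week dosing occurs, -20% or +60%. Weekly or more frequent dosing is unaffected on a per-week basis, and so are the other SAP 6 windows when doses are exactly on schedule.

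The consequence is extra variance in a small pooled comparison, not a systematic shift between arms. How much depends on the share of patients on long intervals, which the documents do not give; if nobody is dosed less often than weekly, this part has no effect.

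The open multiplier is a separate fault. Using 5 against 4 shifts the change from baseline by +25 points in every patient whose regimen is unchanged, whatever the schedule. It drops out where both sides are compared as mean dose per week.

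Both should be corrected before the analysis. Given the endpoint's exploratory status, neither threatens the trial's main conclusions.

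**What to change.** In SAP 6:
1. Put the post-baseline dose on the baseline's footing. Divide each dose by its dosing interval in weeks, assign that amount to each week it covers, carry in the last dose given before the window, and average over the weeks of the window. An unchanged regimen then gives D/k on both sides and 0% change.
2. Fix one multiplier for baseline and post-baseline, or report both per week and drop it.
3. State that Weeks 8-12 means five weeks.

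In SAP 1.2.3.2, restate criterion 14's divide-by-interval rule so that post-baseline ERI is computed as screening ERI is.

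Replacing Weeks 8-12 by the existing Weeks 9-12 would be simpler, but it removes the artefact only under exact schedules: a dose that slips across a boundary still changes the count.

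The cost is SAP wording and a small programming change, using dosing records that the analysis already needs. The interval must be taken from the record or derived from dose dates (the case report form is not shown, so which is possible is unknown), and a rule is needed for held doses so that a hold counts as a reduction and is not smoothed away. No change to patient care is involved.

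### SAP Section 6 puts baseline ESA dose on a 4-week scale but allows a number-of-weeks scale after baseline, so an unchanged dose can read as +25% in the Weeks 8-12 endpoint interval

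*SAP*

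**What the plan says.** All of the relevant text is in SAP Section 6.

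- **Baseline scale.** "The baseline dose will be the baseline mean weekly dose for each ESA as defined below multiplied by 4". The bullets for epoetin alfa and for the two longer-acting ESAs repeat the factor of 4, and a last bullet applies it to the normalized weekly average for all ESAs. No other multiplier is offered.
- **Post-baseline scale.** The dose is built from the sum of doses in the interval, and the weekly average is then "multiplied by 4 or the number of weeks in the interval". Nothing says when each multiplier applies.
- **Intervals.** After the consecutive 4-week blocks, the section adds: "In addition, Weeks 8-12 (the endpoint) and Weeks 1-12 will be described".
- **Analyses.** The first compares mean weekly dose, in epoetin units, before and after randomization. The second is a percent change, by 4-week block: "The percentage change from baseline with all 3 ESAs combined will be calculated". Both bullets then add: "Inferential statistics will be performed for the Week 8-12 and the Week 1-4 periods". The third counts patients whose dose changed by at least 25%, 50% or 100%, "for each 4-week interval in the Treatment and Safety Follow-up periods (e.g. Weeks 1-4, 5-8, etc"), and has no sentence extending it to Weeks 8-12.
- **Parenteral iron.** Post-randomization iron doses are to be summarized along the same lines as ESA doses.

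**The concern.** A percent change is meaningful only if numerator and denominator are on the same time scale. Here the denominator is always a 4-week dose. The numerator may be a 4-week dose or an interval total, since average weekly dose times number of weeks simply returns the sum of the doses. For 4-week blocks the alternative changes nothing. The only intervals in which it has any effect are Weeks 8-12 and Weeks 1-12, and a programmer giving the clause a purpose would apply it there.

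Weeks 8-12 is labelled the endpoint in SAP Section 6 and is the Evaluation Period for ESA dose requirements in Protocol Section 3.1.3. It is one of only two periods with inferential statistics. Protocol Section 3.5.3 expects ESA requirements to fall, and the mismatch pushes the within-arm result upward, so it can mask the expected fall. The same patient data could yield 0% or +25%, depending on a choice the plan leaves open.

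**Working it through.** The documents give no numerical result for this rule, so there is no stated figure to reproduce. The check is direct arithmetic.

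**Length of the interval.** Section 6 calls Weeks 1-4 and Weeks 5-8 4-week intervals, so weeks are counted inclusively. Weeks 8-12 therefore contains Weeks 8, 9, 10, 11 and 12, which is 5 weeks (Days 50 to 84). Weeks 1-12 is 12 weeks.

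**Formula.** Let the baseline weekly dose be d and the true relative change be c. Baseline is 4d. Post-baseline is m x d x (1 + c), where m is 4 or the number of weeks. The apparent change is (m/4)(1 + c) - 1.

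**Unchanged dose (c = 0).**

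| Interval | Weeks | m = 4 | m = number of weeks |
|---|---|---|---|
| 1-4, 5-8, 9-12 | 4 | 0% | 4/4 - 1 = 0% |
| 8-12 | 5 | 0% | 5/4 - 1 = +25% |
| 1-12 | 12 | 0% | 12/4 - 1 = +200% |

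**True changes in Weeks 8-12 with m = 5.** The apparent change is 25% + 1.25c.

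- True -10%: 25 - 12.5 = +12.5%
- True -20%: 25 - 25 = 0% (that is, 0.8 x 5/4 = 1.00)
- True -40%: 25 - 50 = -25%

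**Between-arm percent change.** The same line, 25 + 1.25c, applies to every patient in every arm. The constant 25 cancels in a difference between arms, and the difference and its standard error are both multiplied by 1.25, so the p-value does not move. A simulation on assumed data (48 active, 12 placebo, a true 15% reduction on active, baseline-adjusted) agrees: the difference went from -19.5 to -24.4 percentage points, with p = 0.0014 both times.

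**Change in scaled dose.** With m = 5 this is 5 x post - 4 x baseline, which equals 5 x (post - baseline) + baseline, in weekly doses. Each patient's own baseline leaks into the change. With baseline as a covariate, the treatment coefficient is again only multiplied by 1.25; in the same simulation p stayed at 0.0042. Without that adjustment, a chance baseline imbalance enters the between-arm difference.

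**What does not move.** The first analysis uses mean weekly dose on both sides. The dose-change categories are specified for 4-week intervals, where m = 4 either way. ERI (SAP Section 1.2.3.2) is calculated from the weekly dose.

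**The case against.** The strongest reply is that the error is conditional. The first multiplier listed is 4, and with it every interval gives 0% for an unchanged dose. That is so, but the alternative clause has no effect at all unless it is used in the two intervals where it does harm.

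A second reply is that Weeks 8-12 might mean visit to visit, Day 50 to Day 78, which is 28/7 = 4.0 weeks. The SAP's own labels do not support this: on that reading Weeks 1-4 would run from Day 1 to Day 22, or 21/7 = 3 weeks, yet it is called a 4-week interval.

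A third reply concerns reach, and it stands. A reader might infer four stronger things that the documents do not support:

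- **That every unchanged patient would be counted as a change of at least 25%.** Those counts are specified for 4-week intervals only, where the multipliers agree.
- **That both inferential ESA analyses are affected.** The mean-weekly-dose comparison involves no multiplier, and would expose a discrepancy if set beside the percent change.
- **That a reduction relative to placebo would be hidden.** In percent change it would be enlarged by 1.25 with the same p-value. The masking is within arm. Section 6 does not say whether its inference is within or between arms; a test of within-arm percent change against zero would be directly wrong.
- **That a false +200% would enter a planned test.** Weeks 1-12 is only to be described, and neither percent change nor inference is specified for it.

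Finally, ESA dose requirement is an exploratory endpoint in Protocol Section 3.1.3 and SAP Section 1.2.3.2, so the primary safety and pharmacodynamic results are not touched.

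**Conclusion.** The concern holds within limits. As written, Section 6 permits a Weeks 8-12 percent change that is 25 percentage points too high for an unchanged dose and that shows no change for a true 20% reduction. The affected results are the within-arm percent change and the change in scaled dose for Weeks 8-12, the size (not the p-value) of the between-arm difference in percent change, any percent change computed for Weeks 1-12, and the corresponding parenteral iron summaries.

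This rests on two assumptions: that the number-of-weeks multiplier is the one programmed, and that weeks are counted inclusively, as the SAP's labels imply. It should be corrected before the Weeks 8-12 analyses are programmed, but it does not threaten the trial's main conclusions.

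**What to change.** Either of two edits to SAP Section 6 is enough.

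1. **Smallest change.** In the post-baseline rule, keep the factor of 4 and delete the number-of-weeks alternative. Baseline and every interval, including Weeks 8-12 and Weeks 1-12, are then on one 4-week-equivalent scale.
2. **Cleaner change.** Express baseline and every interval as mean weekly dose in epoetin units, and remove the factor of 4 everywhere it scales a dose in Section 6. It occurs five times: the baseline lead sentence, the two product-specific baseline bullets, the baseline normalization bullet and the post-baseline rule. Removing only some of them could create a worse mismatch; a weekly post-baseline dose against a 4-week baseline would read 1/4 - 1 = -75% for an unchanged dose.

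Under either edit an unchanged dose gives 0% in every interval. State that Weeks 8-12 is five weeks counted inclusively, and apply the same rule to parenteral iron, expressed in mg of elemental iron. The cost is a short SAP edit and, if anything, simpler programming. Data collection, dosing and trial conduct do not change.
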